5.2 Exclusion Criteria

The following are the exclusion criteria; subjects must meet NONE of the following exclusion criteria to be enrolled.

Gastrointestinal exclusion criteria

1. Subject with CD, indeterminate colitis, or presence or history of fistula consistent with CD.

2. History of toxic megacolon, abdominal abscess, symptomatic colonic stricture, or stoma; history of extensive colonic resection, or subtotal or total colectomy; or is at imminent risk of colectomy.
3. History or current evidence of colonic dysplasia or adenomatous colonic polyps.
Note: Subjects will not be excluded from the study because of a pathology finding of indefinite dysplasia with reactive atypia. Subjects with resected adenomatous polyps may be enrolled.

Infectious disease exclusion criteria

4. Current bacterial or parasitic pathogenic enteric infection, including *Clostridium difficile* (confirmed by toxin result), current infection with hepatitis B or C virus (subjects treated for HCV infection must have evidence of sustained virologic response 12 weeks after the end of treatment [SVR12], infection requiring hospitalisation or IV antimicrobial therapy, opportunistic infection within 6 months of dosing, any infection requiring antimicrobial therapy within 2 weeks of dosing, history of more than one episode of herpes zoster, history of infection with human immunodeficiency virus (HIV), or any episode of disseminated zoster. Note: Subjects with a history of *C. difficile* infection treated with antibiotics with or without faecal microbial transplant may be rescreened after 2 weeks following completion of treatment.
5. Live virus vaccination within 1 month prior to screening.

General exclusion criteria

6. Subject has a concurrent clinically significant, unstable, or uncontrolled cardiovascular, pulmonary, hepatic, renal, GI, genitourinary, haematological, coagulation, immunological, endocrine/metabolic, or other medical disorder that, in the opinion of the Investigator, might confound the results of the study or poses additional risk to the subject by their participation in the study.
Note: Subjects with a history of uncomplicated kidney stones, childhood asthma, or concurrent stable and well-controlled asthma may be enrolled in the study at the discretion of the Investigator.
7. Known primary or secondary immunodeficiency.
8. History of myocardial infarction, unstable angina, transient ischaemic attack, decompensated heart failure requiring hospitalisation, congestive heart failure (New York Heart Association Class 3 or 4), uncontrolled arrhythmias, cardiac revascularisation, stroke, uncontrolled hypertension (systolic blood pressure [BP] > 160 mmHg or diastolic BP > 100 mmHg at Screening), or uncontrolled diabetes (haemoglobin A1c > 9% or > 1 episode of severe hypoglycaemia) within 6 months of screening.

9. Clinically meaningful laboratory abnormalities at Screening, including but not limited to, the ranges below:
 - a. Absolute neutrophil count < 1000/ μ L
 - b. Platelet count < 100,000/ μ L
 - c. Haemoglobin < 9 g/dL
 - d. Creatinine \geq 1.5 mg/dL
 - e. alanine aminotransferase or aspartate aminotransferase \geq 2.5 x upper limit of normal (ULN) or bilirubin > 1.5 x ULN
10. Pregnant or lactating females.
11. Any surgical procedure requiring general anaesthesia within 1 month prior to screening, or planned elective surgery during the study.
12. History of malignant neoplasms or carcinoma in situ within 5 years prior to screening. (Subjects who are cancer-free for the previous 5 years may be enrolled. Subjects with adequately treated non-metastatic basal cell skin cancer, squamous cell skin cancer that has not recurred for at least 1 year prior to screening, or history of adequately treated cervical dysplasia/cervical intraepithelial neoplasia or cervical carcinoma in situ that has not recurred at least 3 years prior to screening may be enrolled.)
13. History of any major neurological disorders, as judged by the Investigator, or positive PML subjective symptom checklist.
14. Current or recent history of alcohol dependence or illicit drug use within 1 year prior to screening.
15. Subject is mentally or legally incapacitated at the time of Screening visit or has a history of clinically significant psychiatric disorders that would impact the subject's ability to participate in the trial according to the Investigator. Note: Subjects who have had situational depression or adjustment disorder or treated depression may be enrolled at the discretion of the Investigator.
16. Unable to attend study visits or comply with procedures.
17. Concurrent participation in any other interventional study.

Medication exclusion criteria

18. Use of topical 5-ASA or corticosteroid enemas/suppositories within 2 weeks of administration of the screening endoscopy.
19. Use of TNF- α antagonists within 60 days prior to screening.
20. Use of ustekinumab within 3 months prior to screening.
21. Use of cyclosporine, thalidomide, tacrolimus, sirolimus, or mycophenolate mofetil within 1 month prior to screening.

22. Have received any investigational or biologic agent within 1 month (or 5 half-lives of the agent whichever is longer) prior to screening.
23. Prior treatment with vedolizumab or natalizumab.

5.3 Removal of Subjects from Study Participation

In accordance with the Declaration of Helsinki and other applicable regulations, a subject has the right to withdraw from the study at any time and for any reason without prejudice to his or her future medical care by the physician or at an institution. The Investigator (or designee) may remove a subject from the study if, in the Investigator's (or designee's) opinion, it is not in the best interest of the subject to continue the study. Subjects may be withdrawn due to (but not limited to) any of the following:

- change in compliance with inclusion/exclusion criterion that is clinically relevant and affects subject safety
- at the subject's request (withdrawal of consent)
- protocol noncompliance
- occurrence of AEs that, in the Investigator's opinion, require subject removal
- occurrence of pregnancy
- intake of non-permitted concomitant medication that might affect subject safety or study assessments/objectives.

Notification of withdrawal will be made to the Sponsor as soon as is practical. In case of withdrawal, all reasonable efforts will be made to perform all final study day assessments within 10 days of termination (eg, Early Termination visit) ([Table 6-1](#)). The date the subject is withdrawn from the study and the reason for withdrawal will be recorded on the subject's Case Report Form (CRF). All withdrawn subjects will be followed until resolution of all their AEs or until the unresolved AEs are judged by the Investigator (or designee) to have stabilised.

5.4 Management of Subject Safety

Following dose administration and before leaving the site, each subject will be given a Patient Alert card to carry at all times in case of any emergency outside of the site. The card gives details of the study name and study drug used, name of the relevant Investigator, address and telephone number of the site, as well as emergency out of office contact details if a third party medical professional requires any details or safety information about the study or study drug in case of emergency. Subjects should retain

this card after they have completed or discontinued the study and during the follow-up phase, and destroy the card when directed by study personnel.

6 STUDY PROCEDURES

6.1 Schedule of Study Procedures

A study flow chart is presented in [Table 6-1](#). The total blood volume that will be taken during the study is outlined in [Appendix E](#).

Table 6-1 Study Flow Chart

	Screening	Randomisation Period	Treatment								Follow up		Early Termination ³
	Days -42 to -7	Day -7 to Day -1	Day 0 (pre-dose) ¹	Day 0 (dosing, post-dose)	Day 14 ±3 days	Day 28 ±3 days	Day 42 ±3 days	Day 56 ±3 days	Day 70 ² ±3 days	Day 84 ±3 days	Day 112 ±7 days	Day 252 ² ±30 days	
Informed Consent	X												
Demographics	X												
Medical History	X												
Prior and Concomitant Medications ⁴	X		X	X	X	X	X	X	X	X	X		X
Inclusion/Exclusion	X												
Height	X												
Weight	X		X		X	X	X	X		X	X		X
Physical Examination ⁵	X		X	X	X	X	X	X		X	X		X
Vital Signs ⁶	X		X	X ⁷	X	X	X	X		X	X		X
12-lead ECG ⁶	X		X ⁸		X			X		X	X ⁹		X
Laboratory: Haematology, Coagulation, Serum Chemistry ¹⁰	X		X		X	X		X		X	X		X
Stool C.diff , Culture, and Ova and Parasites	X												
Urinalysis (microscopy if abnormal)	X		X		X	X		X		X	X		X
PML Neurological Assessment ¹¹	X		X		X	X	X	X	X	X	X	X	X
Hepatitis B & C; TB Test	X												
Serum Pregnancy (WOCBP)	X									X	X		X

	Screening	Randomisation Period	Treatment								Follow up		Early Termination ³
	Days -42 to -7	Day -7 to Day -1	Day 0 (pre-dose) ¹	Day 0 (dosing, post-dose)	Day 14 ±3 days	Day 28 ±3 days	Day 42 ±3 days	Day 56 ±3 days	Day 70 ² ±3 days	Day 84 ±3 days	Day 112 ±7 days	Day 252 ² ±30 days	
Sigmoidoscopy	X ¹²									X			X
Colonic Biopsy	X ¹²									X			X
Mayo Score ¹³	X ¹²				X	X	X	X	X	X	X		X
JCV Antibody Testing ¹⁴	X ¹⁴												
Confirmation of Eligibility			X										
Randomisation ¹⁵		X											
Adverse Events			X	X	X	X	X	X	X	X	X		X
IBDQ			X							X			X
Faecal Calprotectin			X				X			X	X		X
Urine Pregnancy (WOCBP)			X		X	X	X	X					
PK Blood Collection ¹⁶			X	X ¹⁷	X	X	X	X		X ¹⁷			X ¹⁷
PD Blood Collection ¹⁶			X	X ¹⁷	X	X	X	X		X ¹⁷			X ¹⁷
ADA Testing			X			X		X		X	X		X
Exploratory Immunologic Assessment Blood Sample ¹⁸			X										
IP Administration ¹⁹				X	X	X	X	X	X	X			

ADA = anti-drug antibodies; AE = adverse event; ECG = electrocardiogram; IBDQ = Inflammatory Bowel Disease Questionnaire; IP = investigational product; JCV= John Cunningham virus; PD = pharmacodynamics; PK = pharmacokinetics; PML = progressive multifocal leukoencephalopathy; TB = tuberculosis; WOCBP = women of childbearing potential.

¹ All predose procedures should be completed prior to dosing.

² Day 70 AE monitoring will be obtained via phone call and data to calculate rectal bleeding and stool frequency subscores will be obtained; 6-month follow-up PML assessment will be obtained via phone call (the phone call should occur 6 months following discontinuation of treatment if the subject terminates early).

³ Procedures to be performed within 10 days of Early Termination.

⁴ All prior medications taken within 3 months before Screening should be recorded.

⁵ Complete physical examinations (including a neurological examination) should be conducted at Screening. Complete physical examinations should also be conducted at Day 84, Day 112, and/or Early Termination. Directed physical examinations should be conducted at other time points. The Day 0 postdose examination will occur 4 hours postdose.

⁶ Participants should be rested in a supine or semi-recumbent position for ≥ 5 minutes prior to recording of ECGs and vital signs. The ECGs and vital signs should be assessed prior to blood draws. Temperature by oral, axillary, or tympanic route may be permitted provided the same route is used for the participant throughout the study.

⁷ Vital signs will be done at 1, 2, and 4 hours ± 20 minutes postdose following the first dose of study drug.

⁸ Predose (baseline) ECGs should be repeated 3 times with 1- to 2-minute intervals between ECG readings, all within 2 hours prior to dosing.

⁹ ECG only to be performed if previously abnormal.

¹⁰ Laboratory samples collected at Screening and on Day 0 (predose), Day 28, Day 84 (or Early Termination), and Day 112 MUST be after the participant has FASTED from all food and drink except water for ≥ 8 hours (except for any dietary requirements that are part of sigmoidoscopy prep). Chemistry Panel at these fasting visits will include cholesterol and glucose analytes. All other non-fasting visits will have Chemistry Panel completed without cholesterol and glucose analytes. See [Appendix B](#) for list of analytes assessed.

¹¹ PML Assessment Questionnaire subjective checklist will be performed at Screening and at designated study visits (see [Appendix D](#)). If the Screening PML subjective checklist was performed within 14 days of Day 0, it will not need to be repeated on Day 0. At Day 0 (predose), subjects will be educated on the signs and symptoms of PML and advised to report if they experience any of those signs or symptoms at any time during the study.

¹² Sigmoidoscopy, biopsy, and a baseline complete Mayo Score are to be completed within 14 days of randomisation (as close to randomisation as possible; however, subjects may have a combined Screening visit that includes endoscopy) after confirmation of eligibility from other screening tests. Mayo Score for stool frequency and rectal bleeding should be done before the day of sigmoidoscopy. Mayo Score for physician's global assessment will be completed on the day of the sigmoidoscopy. Sigmoidoscopy should be the last procedure before randomisation. Subjects must meet eligibility criteria of Mayo Score 6 to 12 and endoscopy subscore of ≥ 2 in order to be randomised.

¹³ Complete Mayo Score (including all 4 subscores) to be assessed at Screening, Day 84, and Early Termination (if possible); partial Mayo Score (without endoscopy subscore) to be assessed at all other time points except Day 70 where only rectal bleeding and stool frequency subscores will be reported via phone.

¹⁴ JCV antibody testing must be performed within 90 days prior to dosing. Testing will be performed at the time of the pretreatment sigmoidoscopy if no prior results (within the 90-day timeframe) are available, and if the subject is eligible for study enrolment. Results will not determine eligibility for the trial.

¹⁵ Randomisation will occur after all subject eligibility has been confirmed in the screening period. Randomisation in the interactive web/voice response system must be completed in advance of Day 0. Dosing should occur within 7 days of randomisation.

¹⁶ Baseline (Day 0 predose) PK and PD blood samples will be taken within 2 hours prior to dosing. PD samples to be taken at selected sites only.

¹⁷ PK samples are to be collected at 1, 2, and 4 hours ± 20 minutes postdose on Day 0 and Day 84 or Early Termination (if possible) only. PD samples to be collected 4 hours ± 20 minutes postdose on Day 0 and Day 84 or Early Termination (if possible) only. For every visit other than Day 0, a single PK and PD sample will be obtained within 1 hour prior to taking the regularly scheduled dose.

¹⁸ A separate blood sample will be collected at selected sites (Day 0 predose only) for immunologic assessment.

¹⁹ IP will be administered once daily for 84 days. The first drug will be administered at the study centre and subjects will be observed for at least 4 hours. On visits to study site, subjects should take the daily dose of study medication after completion of all blood collections. On Day 0, if the IP shipment is delayed, late dosing will not be considered a protocol deviation.

6.2 Study Treatment

6.2.1 Drug Supplies and Accountability

Specific instructions about the storage, dispensation, and administration of PTG-100 to subjects will be provided in the pharmacy manual.

The Sponsor (or designee) will provide the Investigator (or designee) with adequate quantities of the study drugs (Table 6-2).

Table 6-2 Study Drug

Study Drug	Placebo	PTG-100	PTG-100
Form^a	Powder in a hard gelatin capsule	Powder in a hard gelatin capsule	Powder in a hard gelatin capsule
Strength	0 mg	150 mg	300 mg
Supplier	Protagonist	Protagonist	Protagonist
Manufacturer	Catalent	Catalent	Catalent

^a Specific ingredients/purity will be identified in the Certificate of Analysis (or equivalent) that is supplied with the study drug.

The lot numbers for the study drug will be provided to the clinical sites by the supplier/manufacturer.

Study drugs will be supplied in blister packs and **stored refrigerated at 2°C to 8°C under secure conditions.**

The Investigators (or designees) will maintain an accurate record of the receipt of the clinical trial materials as shipped by the Sponsor (or designee), including the date received. One copy of this receipt will be returned to the Sponsor (or designee) when the contents of the shipment have been verified. In addition, an accurate drug disposition record will be kept, specifying the amount dispensed to each subject and the date of dispensation. This drug accountability record will be available for inspection at any time. At the completion of the study, the original drug accountability record will be available for review by the Sponsor on request.

At the completion of the study, all unused drug supplies will be returned to the Sponsor (or designee) or disposed of by the clinical site(s), per the Sponsor's (or designee's) written instructions.

6.2.2 Subject Number and Identification

Subjects will be assigned a number by an Interactive Web Response System . Assignment of numbers will be in ascending order and no numbers will be omitted. Subject numbers will be used on all study documentation. For subjects who are withdrawn by the Investigator (or designee) or who voluntarily withdraw prematurely from the study, replacement subjects will be enrolled only if deemed necessary by the Sponsor. Replacement subjects will be assigned a subject number by adding 300 to the number of the subject they are replacing (eg, Subject No. 305 replaces Subject No. 005) and will be enrolled into the same randomisation arm as the subject whom they are replacing.

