6.2.4 Blinding

This will be a double-blind, placebo-controlled study. As such, the Sponsor, CRO, Medical Monitors, Investigator, site pharmacist (or designee), site personnel involved in study conduct, and subjects will remain blinded to study medication assignment.

An independent Data Monitoring Committee (DMC) will monitor safety throughout the study period and may be unblinded as necessary. Limited personnel required for conducting the analyses may also be unblinded to allow necessary safety oversight. The DMC will also be involved in the IA. Limited personnel required for conducting the IA will also be unblinded. Unblinded personnel required for the IA will be defined in the DMC charter.

Unblinding of individual subject treatment assignment may be permitted in the event of an emergency situation requiring knowledge of treatment assignment; however, subject assignment should not be routinely unblinded. Unblinding will be performed via the IXRS. This randomisation information may be opened and the randomisation for each individual subject made available to the Investigator (or designee) only in the event of a medical emergency or an AE that necessitates identification of the clinical trial material for the welfare of that subject. Except in a medical emergency, the Investigator (or designee) and blinded clinical site staff will remain blinded during the conduct of the study and until such time that all discrepancies in the clinical database are resolved (ie, at the database lock). The date/initials and reason for the Investigator (or designee) removing the study blind will be documented. Although the Investigator (or designee) will remain blinded as to treatment, the Investigator (or designee) will assess the data in

aggregate for safety and tolerability review. Unblinding for any other reason will be considered a protocol violation.

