7.2 Interim Analysis

An unblinded IA will be performed by the Adaptive Design Review Committee (ADRC) after approximately 60 to 80 subjects have been dosed and completed 12 weeks of dosing or terminated early (Stage 1).²³ A futility analysis will be performed; if the trial does not meet criteria for futility, further analysis will be conducted in order to drop one (or 2) of the PTG-100 dose arms (Stage 1, see below). Following the IA, randomisation will continue to the remaining dose arms (Stage 2).

Conditional power will also be computed at the IA. It is the probability that the trial will yield a statistically significant difference for clinical remission at the higher chosen dose for Stage 2 if the observed difference at the IA is the TRUE underlying difference and the trial is continued to completion. If this probability is low (eg, less than 10% to 20%), the decision could be made to stop the trial for futility.

The PD, efficacy, and safety data will be analysed to model dose- and exposure-response from Stage 1 of the trial to allow dropping of an ineffective or redundant arm(s). Since the trial provides for a 12-week treatment period, it is expected that an additional approximately 60 subjects would be randomised in equal proportions to the 4 treatment groups while the first approximately 60 to 80 subjects' 12-week data are accumulated and analysed. Hence, in Stage 2, the remaining subjects would be randomised in equal proportions to the selected dose(s) and placebo. This would yield approximately 70 to 80 subjects per treatment group for the selected doses. Final analysis will combine all observed data from both Stages 1 and 2.

The IA guidelines for futility and dose selection will be defined in the DMC charter and will be made in consideration of safety data and sound clinical judgment. Dose selection for Stage 2 will be made by the ADRC, which will be comprised of the DMC and a representative of the Sponsor (not involved in the direct conduct of the study). No pre-specified algorithm will be defined for the IA, although specific guidelines for dropping a dose(s) will be provided in the DMC charter. Only the ADRC, which will make the dose selection for Stage 2, and the Independent Statistical Centre, which will perform the IA, will be unblinded.

Stratification by prior treatment with TNF- α antagonist use will be maintained in both Stage 1 and 2.

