Multiplicity will be addressed via closed testing procedure with combined p-values computed for each of the 2 stages of the trial (IA and post-IA). Each stage p-value will be adjusted as appropriate by closed testing multiple comparison approach per Simes.²⁴ This approach controls the overall type 1 error at $\alpha=0.025$, 1-sided.

All analyses will be based on combined Stage 1 and Stage 2 data and include data from the dose(s) that is (are) dropped for Stage 2. Exploratory analyses will be carried out to assess consistency of results between Stages 1 and 2. Analyses of other binary endpoints will be carried out similarly.

Subjects who discontinue prematurely will be considered treatment failures.

Changes from baseline complete Mayo Score, partial Mayo Score, rectal bleeding subscore, stool frequency subscore, endoscopic subscore, IBDQ score, and faecal

calprotectin levels will be analysed using repeated measures mixed analysis of covariance model adjusted for treatment, time point, treatment-by-time point interaction, stratification factors, and baseline values. For subjects who withdraw prematurely, the last observation will be carried forward. These analyses will be based on the Stage 1 and Stage 2 combined data for exploratory purposes.

Details regarding the statistical analyses of efficacy data will be provided in the Statistical Analysis Plan (SAP).

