#### 4.2.7. Withdrawals, Dropouts, Loss to Follow-up

For subjects who are withdrawn by the Investigator (or designee) or who voluntarily withdraw prematurely from the study, replacement subjects will be enrolled only if deemed necessary by the sponsor. Replacement subjects will be assigned a subject number by adding 300 to the number of the subject they are replacing (e.g., Subject No. 305 replaces Subject No. 005) and will be enrolled into the same randomization arm as the subject whom they are replacing.

Analyses will utilize all available data obtained from such subjects (withdrawn and replacement subjects), in accordance with the study population definitions.

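### Replacement subjects are placed in the withdrawn subject's arm instead of being randomised, which conflicts with the Stage 2 allocation rule and, after a code break, can disclose an assignment

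*Protocol*

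**What the plan says.** Protocol 6.2.2 and SAP 4.2.7 carry the same rule. After a withdrawal, "replacement subjects will be enrolled only if deemed necessary by the Sponsor"; no criterion, cap or closing date is attached. A replacement "will be enrolled into the same randomisation arm as the subject whom they are replacing" (in the SAP: "will be enrolled into the same randomization arm as the subject whom they are replacing"). The identifier is derived from the predecessor's: "Replacement subjects will be assigned a subject number by adding 300 to the number of the subject they are replacing", so that 305 stands in for 005.

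The text that this rule has to fit with is as follows.

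- Protocol 7.2: once doses are chosen, "the remaining subjects would be randomised in equal proportions to the selected dose(s) and placebo", with anti-TNF stratification kept in both stages. The synopsis likewise confines randomisation after dose selection to the arms still open.
- Protocol 7.3 and SAP 3.1: every analysis set starts from randomised subjects who took study drug. The Full Analysis Set (FAS) also needs a baseline result and at least one later result.
- SAP 4.2.7: "Analyses will utilize all available data obtained from such subjects (withdrawn and replacement subjects), in accordance with the study population definitions".
- Protocol 7.4: "Subjects who discontinue prematurely will be considered treatment failures". SAP 4.2.8 applies this to the four binary endpoints.
- Protocol 6.2.4: "Unblinding of individual subject treatment assignment may be permitted in the event of an emergency situation"; an adverse event that makes identification necessary also qualifies. Protocol 5.3 lists adverse events among the reasons for withdrawal.

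**The concern.** A subject's arm should be settled by chance at entry. Under this rule it is settled by which earlier subject left, and so by withdrawal in that arm, which may be related to treatment. Three consequences follow. Subjects not assigned by chance enter analysis sets defined on randomised subjects. An arm closed at the interim analysis can be reopened one subject at a time. And the +300 number is a visible link between two subjects known to share a treatment, which matters once either assignment has been disclosed. The trial has a confirmatory one-sided test at 0.025, so the basis for comparing arms should not depend on a discretionary refill rule.

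**Working it through.** **What the plan gives.** The plan states no withdrawal rate, no replacement rate and no allowance for either in the sample size (Protocol 7.1, SAP 4.1). The planned N of 240 is meant to carry the power by itself. A simulation of the two-stage design at N=240 without replacements (60 in Stage 1, 60 overrun, the two best doses kept, Simes closed test with inverse-normal combination, 40,000 trials) gives 89.5% and 80.5%. The plan states 91% and 82%. With 80 in Stage 1 it gives 88.7% and 79.2%. The stated figures come from 1,000 simulations, so the first has a standard error of √(0.91×0.09/1000) = 0.9 points. The point below does not rest on power.

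**Step 1. The two allocation rules side by side.** Suppose a subject in a dose arm withdraws, the dose is dropped at the interim analysis, and the sponsor then decides to replace. Section 6.2.2 sends the new subject to the dropped arm. Section 7.2 sends every new subject to a selected dose or placebo. Neither document says which governs. Under SAP 4.6.1 the Stage 1 component takes subjects enrolled up to the data snapshot, and the Stage 2 component takes later subjects in continuing arms only. A replacement enrolled into a dropped arm after the snapshot falls in neither.

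**Step 2. How likely the conflict is, if replacement is used.** Size of a dropped arm = (Stage 1 + overrun)/4, from Protocol 7.2: (60+60)/4 = 30 to (80+60)/4 = 35. With an assumed withdrawal rate d, expected withdrawals are n×d and P(at least one) = 1−(1−d)^n.

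| d (assumed) | Expected, n=30 | P(≥1) | Expected, n=35 | P(≥1) |
|---|---|---|---|---|
| 5% | 1.5 | 78.5% | 1.75 | 83.4% |
| 10% | 3.0 | 95.8% | 3.5 | 97.5% |
| 20% | 6.0 | 99.9% | 7.0 | >99.9% |

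If every added subject were randomised to the arms then open, entries into a dropped arm would be 0.

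**Step 3. Total not assigned by chance.** Number = 240 × d × share replaced. With none replaced it is 0. With all replaced it is 24 at 10% and 36 at 15% (12 at 5%, 48 at 20%).

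**Step 4. Balance.** With 70 per arm and full replacement, an arm with 20% withdrawal grows to 70×1.20 = 84, and one with 10% to 70×1.10 = 77. Arm sizes follow withdrawal. The stratum can drift too, since no match is required.

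**Step 5. Remission rate.** Let r be the arm's rate with withdrawals counted as failures. Replace each of n×d withdrawals once with a subject of the same prognosis, and keep the withdrawn subject as a failure. The expected rate is (n×r + n×d×r)/(n + n×d) = r. For n=70, r=10%, d=20%: (7.0+1.4)/84 = 10.0%. Letting the number of withdrawals vary (400,000 simulated arms) gives 10.01% without replacement and 10.02% with it.

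**Step 6. Disclosure.** Before enrolment, someone who knows only that four arms are open at equal allocation has a 1 in 4 chance of naming a subject's arm. Someone who knows the predecessor's broken code and sees the +300 number is certain of it. Matching capsules do not remove that knowledge.

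**Step 7. Numbering.** Section 6.2.2 also requires numbers to be given in ascending order without gaps. A +300 offset does not fit that sentence.

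**The case against.** The strongest case against is that the rule may never operate, and does little harm if it does.

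- Replacement is optional. This stands: the lower end of the range is 0, and 24-36 is a ceiling for the assumed withdrawal rates.
- The sponsor is blinded apart from its representative on the Adaptive Design Review Committee, who takes no direct part in running the study. A reader might infer from the sponsor's discretion that arms could be refilled selectively. The documents do not support that. What remains is that arm sizes follow withdrawal without anyone choosing.
- Disclosure needs a code break, a withdrawal, a decision to replace, and someone who knows the code and sees the new number. That is most likely at the same site, and 6.2.2 does not say the replacement comes from there. With 100 to 120 sites and 240 subjects the average is 2.0 to 2.4 per site. The route is real but conditional; the rule does not reveal treatment as a matter of course.
- The primary Cochran-Mantel-Haenszel test is stratified by prior anti-TNF use, so an unmatched replacement is analysed in its own stratum. This stands: the missing match costs balance and does not put subjects in the wrong stratum.
- A reader might infer that replacement is pointless because withdrawn subjects stay in as failures. That goes too far. A subject with no post-baseline result leaves the FAS, and the failure rule covers only the binary endpoints. Extra subjects can have a use, but randomised ones would serve it.
- A one-line exception for dropped arms would end the conflict with 7.2. It would not make the other replacements random or break the number link, and refusing replacement for certain subjects would point to who had been in a dropped arm.

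**Conclusion.** The point holds as a fault in a stated rule. The same-arm rule is not random allocation, contradicts the Stage 2 allocation in Protocol 7.2 when a dose has been dropped, and ties pairs of subjects together in a way that can pass on a broken code. It should be corrected, though it does not threaten the trial as a whole.

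The size is 0 to about 24-36 subjects, assuming 10-15% of 240 withdraw and up to all are replaced. If replacement is used throughout, 1.5 to 7 entries per dropped arm are expected at 5-20% withdrawal. These rates are assumptions.

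A reader might infer a biased remission rate or an inflated type 1 error. Neither is shown. With discontinuations kept as failures and replacements of like prognosis, the rate hardly moves, and a late entry into a dropped arm reaches neither component of the final p-value. The harm is to random allocation, balance and blinding.

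**What to change.** Delete the same-arm and +300 rules from Protocol 6.2.2 and SAP 4.2.7. State instead that withdrawn subjects are not replaced one for one. If more subjects are needed, including to make up for those who leave the FAS, they receive the next sequential number and are randomised by the IXRS, within the anti-TNF stratum, to the arms open at that time. Withdrawn subjects who meet the FAS definition stay in as failures for the binary endpoints.

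The text is a few sentences, plus an IXRS setting. A protocol change also needs agreement between sponsor and investigators and handling by the ethics committees (Protocol 8.1 and 8.6) across the planned 100 to 120 sites, so it is best carried with another amendment if one is due. Planned N and power do not change, because replacements were never counted in them. The price is that an arm which loses subjects from the FAS is no longer refilled directly; any allowance for that belongs in the sample size.
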